6 SELECTION OF SUBJECTS

The following subject will be screened:

- Male or female, (Grade 1-2), uncontrolled hypertensive patients ≥18 and ≤65 years of age
- Considering a screening failure and a drop-out rate of 25%, the overall number of patients to be screened is 290.
- 216 patients needed to complete the run-in period and enter the assessment period to guarantee powered results

6.1 Informed Consent Process

Prior to the subject's enrolment into the study and before performing any study-related procedures, the Investigator - or its authorized delegate - shall obtain the subject's written, dated and signed informed consent to participate into the study and process personal data for processing and transferring necessary documentation of the subject's health and personal data to the CRO, Sponsor and its Affiliates, the competent Health Authorities and any other institutions, as legally required and in accordance with the local applicable privacy laws (for the Privacy information to be reported on the ICF refer to Section 17 PERSONAL DATA PROTECTION).

Institution and Investigator undertake to duly inform subjects about personal data processing and the relevant applicable privacy rights before their participation into the study.

After being duly informed and interviewed by the Investigator, . The subject freely has to date and sign the ICF before being enrolled into the study and before undergoing any study procedure. The Investigator must store the originally signed ICF in the Investigator's File, and the subject will be provided with a copy of it.

If a protocol amendment would affect the terms of the ICF, it will be revised to reflect the protocol change and submitted to EC for approval.

The Investigator will ensure that this new consent form is signed by all subjects subsequently entered in the study and those currently in the study, if affected by the amendment.

6.2 Inclusion and Exclusion Criteria

6.2.1 Inclusion Criteria

МЕМАТИИ	Corporate Medical Department		
Identification Number	Version Number	State	Effective date
FORM-000050125	2.0, CURRENT	Effective	08, Jan 2021

Sponsor: Menarini International Operations Luxembourg SA Study Code: MEIN/20/ZoAm-Hyp/001	Protocol Version 1.0 of 1	23/04/2021

A patient will be considered eligible for inclusion in the study only if all the following criteria are met:

- 1. Male or female Grade 1-2 hypertensive patients: with mean sitting SBP ≥140 mmHg and ≤179 mmHg and/or mean sitting DBP ≥ 90 mmHg and ≤109 mmHg at Screening, with ≥18 and ≤65 years of age, on monotherapy either with ZOF 30 mg or AML 5mg or any other ACE-I or CCBs (Felodipine, isradipine, lacidipine, lercanidipine, nicardipine, nifedipine, and nisoldipine) for at least 1 month before Visit 1 (Screening).
- 2. Patients who are able to understand and give written informed consent at Screening
- 3. Patients who are available for the entire trial period and willing to adhere to the protocol requirements
- 4. Ability to take oral medication and willing to adhere to the drug regimen
- 5. Female patients are eligible to participate if not pregnant, or not breastfeeding and must refrain from donating or storing eggs. For females of reproductive potential: use of highly effective contraception (e.g., method of birth control throughout the study period and for 4 weeks after study completion defined as a method which results in a failure rate of less than 1% per year) such as:
 - Combined (estrogen- and progestogen-containing) hormonal contraception associated with inhibition of ovulation (oral, intravaginal, transdermal)
 - Progestogen-only hormonal contraception associated with inhibition of ovulation (oral, injectable, implantable)
 - Intrauterine device (IUD)
 - Intrauterine hormone-releasing system (IUS)
 - Bilateral tubal occlusion
 - Vasectomized partner (performed at least 2 months before screening) (if the partner is the sole sexual partner of the trial participant and that the vasectomized partner has received medical assessment of the surgical success)
- 6. A male patient must agree to use contraception during the whole study period and for at least 1 week after the last dose of study treatment and refrain from donating sperms during this period

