	assessment period to guarantee powered results		
	assessment period to guarantee powered results		
	Inclusion Criteria		
	A patient will be considered eligible for inclusion in the study only if		
Study Population:	all the following criteria are met:		
Subjects	1. Male or female Grade 1-2hypertensive patients: with mean		
characteristics	sitting SBP ≥140 mmHg and ≤179 mmHg and/or mean sitting		
Number of	DBP ≥ 90 mmHg and ≤109 mmHg at Screening, with ≥18		
Subjects	and ≤65 years of age, in monotherapy either with ZOF 30 mg		
	or AML 5 mg, or any other ACE-I or CCBs (Felodipine,		
	isradipine, lacidipine, lercanidipine, nicardipine, nifedipine,		
	and nisoldipine) for at least 1 months before Visit 1		
	(Screening).		
	2. Patients who are able to understand and give written informed		
	consent at Screening		
	3. Patients who are available for the entire trial period and willing		
	to adhere to the protocol requirements		
	4. Ability to take oral medication and willing to adhere to the drug		
	regimen		

Protocol Version 1.0 of 1 23/04/2021

[figure not shown]
Study Code: : MEIN/20/ZoAm-Hyp/001

- 5. Female patients are eligible to participate if not pregnant, or not breastfeeding and must refrain from donating or storing eggs. For females of reproductive potential: use of highly effective contraception (e.g., method of birth control throughout the study period and for 4 weeks after study completion defined as a method which results in a failure rate of less than 1% per year) such as:
 - Combined (estrogen- and progestogen-containing) hormonal contraception associated with inhibition of ovulation (oral, intravaginal, transdermal)
 - Progestogen-only hormonal contraception associated with inhibition of ovulation (oral, injectable, implantable)
 - Intrauterine device (IUD)
 - Intrauterine hormone-releasing system (IUS)
 - Bilateral tubal occlusion
 - Vasectomized partner (performed at least 2 months before screening) (if partner is the sole sexual partner of the trial participant and that the vasectomized partner has received medical assessment of the surgical success)
- 6. A male patient must agree to use contraception during the whole study period and for at least 1 week after the last dose of study treatment and refrain from donating sperms during this period

Exclusion Criteria

Any patient who meets any of the following criteria will not qualify for entry into the study:

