screening visit. Patients previously receiving ZOF 30 mg or AML 5 mg will continue the same treatment, patients receiving other ACE-i will be switched to ZOF 30 mg, while patients receiving CCBs will receive AML 5 mg. Patients entering this phase in therapy with ZOF 30 mg or AML 5 mg should be in a 1:1 ratio. Assessment period from Visit 2 (Week 0) to Visit 4 (Week 8): patients having uncontrolled BP at Visit 2, will be assigned to the extemporaneous combination of ZOF 30 mg and AML 5 mg. After 4 Weeks \pm 2 days the BP will be assessed again (Visit 3): controlled patients (SBP/DBP ≤ 130/80 mmHg) will continue the same extemporaneous combination, while uncontrolled (SBP/DBP >130/80 mmHg) patients will be up-titrated from extemporaneous combination ZOF/AML 30/5 mg to extemporaneous combination of ZOF/AML 30/10 mg for further 4 weeks \pm 2 days (Visit 4, Week 8). At Visit 2 and Visit 3 patients with SBP/DBP value classified as Grade 3 (SBP \geq 180 or DBP \geq 110 mmHg) hypertension will be withdrawn from the study. *To be enrolled in the study, patients could be in monotherapy with one of the listed CCBs: felodipine, isradipine, lacidipine, lercanidipine, nicardipine, nifedipine, and nisoldipine. The primary endpoint will be assessed before and after assessment period at Week 8, by a paired t-test using the Intention-to-treat (ITT) Statistical population and the Per-Protocol (PP) population. Assumptions All the other continuous secondary/exploratory endpoints will be assessed before (Week 0) and after treatment (at Week 8) by a paired t-test. All secondary/exploratory endpoints related to proportion of patients achieving the BP goal at Week 4 and Week 8 will be analysed descriptively producing also the relative 95% CI to assess if there is a significant difference from Week 0 where all patients were uncontrolled.

[figure not shown]
немъни	Corporate Medical Department		
Identification Number	Version Number	State	Effective date
FORM-000050125	2.0, CURRENT	Effective	08, Jan 2021

Protocol Version 1.0 of 1 23/04/2021

Study Code: : MEIN/20/ZoAm-Hyp/001

A total sample size of 216 patients is required to achieve 90% power at a 5% significance level assuming a difference in mean DBP from baseline (Visit 2) to 8 weeks (Visit 4) of 4 mmHg and a standard deviation (SD) for this difference of 10 mmHg. The mean change in DBP for the null hypothesis is set equal to 2 mmHg.

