2.1 Study Scheme

There is not a randomization procedure

§Allowed CCBs at screening: Felodipine, isradipine, lacidipine, lercanidipine, nicardipine, nifedipine, and nisoldipine.

Subjects treated with Amlodipine 10 mg or Zofenopril other than 30 mg will not undergo screening procedures.

Grade 1-2 hypertensive patients mean: Blood pressure [BP] ranging from ≥140/90 mmHg to ≤179/109 mmHg)

МЕМАЯМ	Corpo	orate Medical Departme	nt
Identification Number	Version Number	State	Effective date
FORM-000050125	2.0, CURRENT	Effective	08, Jan 2021

Uncontrolled patients with Grade 1-2 hypertension mean: Sitting SBP/DBP > 130/80 mmHg. Patients with Grade 3 (SBP \geq 180 or DBP \geq 110 mmHg) hypertension will be withdrawn from the study at Visit 2 and Visit 3 Controlled patients mean: SBP/DBP \leq 130/80 mmHg

MENARINI	Согр	porate Medical Departmo	ent
Identification Number	Version Number	State	Effective date
FORM-000050125	2.0, CURRENT	Effective	08, Jan 2021

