5 STUDY DESIGN

This is a phase IV, open-label, multicentre, multinational study with 2 study periods: a 4-week run-in period and an 8-week assessment period.

Approximately 290 patients are planned to be screened to ensure at least 216 patients complete the run-in period and start with the assessment period.

Patients with Grade 1-2 hypertensive patients (blood pressure [BP] ranging from ≥140/90 mmHg to ≤179/109 mmHg) on treatment with any angiotensin converting enzyme inhibitors (ACE-i) including Zofenopril 30 mg or with calcium channel blockers (CCBs) including Amlodipine 5 mg will be screened for eligibility (Visit 1).

Allowed CCBs: Felodipine, isradipine, lacidipine, lercanidipine, nicardipine, nifedipine, and nisoldipine. Patients treated with other dosages of Zofenopril (other than 30 mg) are not allowed to be screened.

After screening, on the same day, eligible patients, will enter into a 4-week run-in period, during which patients on other ACE-i will be assigned to monotherapy with ZOF 30 mg while patients on CCBs[§] will be assigned to monotherapy with AML 5 mg for 4 weeks. Patients with on-going treatment zofenopril 30 mg and amlodipine 5mg will continue on the same treatment for 4 weeks.

After the run-in period (4 weeks \pm 2 days), BP will be further assessed (Visit 2), if BP levels are over the defined controlled target goal (sitting SBP/DBP >130/80 mmHg), treatment is well tolerated and adherence to the treatments ranges from 80% to 120%, patients will enter the assessment period, where they will be assigned to the extemporaneous combination of ZOF 30 mg and AML 5 mg. At Visit 2 patients with SBP/DBP values classified as Grade 3 (SBP \geq 180 or DBP \geq 110 mmHg) hypertension will be withdrawn from the study.

If patients, at Visit 2, after the run-in period, have a controlled BP (sitting SBP/DBP≤130/80 mmHg) or do not tolerate the treatment or have an adherence range below 80% or superior to 120%, they will be withdrawn from the study.

The patients will be assessed for further 8 weeks (assessment period).

After 4 weeks \pm 2 days from Visit 2, during the assessment period patients receiving the extemporaneous combination of ZOF 30 mg and AML 5 mg, will be further evaluated (Visit 3): controlled patients (sitting SBP/DBP \leq 130/80 mmHg) will continue the same

MENARINI	Corporate Medical Department		
Identification Number	Version Number	State	Effective date
FORM-000050125	2.0, CURRENT	Effective	08, Jan 2021

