extemporaneous combination for additional 4 weeks \pm 2 days, while uncontrolled patients (sitting SBP/DBP >130/80 mmHg) will be up-titrated from ZOF/AML 30/5 mg to ZOF/AML 30/10 mg for further 4 weeks \pm 2 days.

At Visit 3 patients with SBP/DBP values classified as Grade 3 (SBP \geq 180 or DBP \geq 110 mmHg) hypertension will be withdrawn from the study.

If patients at Visit 3, do not tolerate the extemporaneous combination treatment or they have an adherence range below 80% or superior to 120%, they will be withdrawn from the study. At the end of the assessment period (8 weeks \pm 4 days) at Visit 4, the anti-hypertensive effect of the extemporaneous combination (ZOF/AML 30/5 mg and ZOF/AML 30/10 mg) will be evaluated.

Efforts will be made to achieve 1:1 ratio in the enrolment of patients receiving any ACE-i or allowed CCBs (refer to section Subject Study Phases Duration for allowed CCBs). At Visit 2, a minimum of 45% of uncontrolled patients receiving treatment with ZOF 30 mg or AML 5 mg are required to enter the assessment period, in order to maintain a balance between the 2 treatments during the assessment period.

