Participants with uncontrolled BP (>130/80 mmHg) will be provided with ZOF 30 mg and AML 5 mg while participants with controlled BP (≤130/80 mmHg) will be withdrawn from the study

Each trial participant is provided with one treatment Patient Kit made up by

- ZOF 30 mg: one labelled box (white label) containing 42 film-coated tablets (3 blisters with 14 film coated tablets each) of zofenopril calcium 30 mg
- AML 5 mg: one labelled box (white label) containing 42 tablets (3 blisters with 14 tablets each) of amlodipine 5 mg.

The two white labelled boxes are then sealed together into a transparent plastic film to realize the treatment Patient Kit.

Trial participant must be carefully instructed by Investigator to take simultaneously (at the same time): ZOF 30 mg (zofenopril calcium 30 mg) as one oblong film-coated tablet and AML 5 mg (amlodipine 5 mg) as one round tablet, according to Study Protocol.

Visit 3 (Assessment)

Participants with controlled BP (≤130/80 mmHg) are provided with one treatment kit made up by:

- ZOF 30 mg: one labelled box (white label) containing 42 film-coated tablets (3 blisters with 14 film coated tablets each) of zofenopril calcium 30 mg
- AML 5 mg: one labelled box (white label) containing 42 tablets (3 blisters with 14 tablets each) of amlodipine 5 mg.

The two white labelled boxes are then sealed together into a transparent plastic film to realize the treatment kit.

Trial participant must be carefully instructed by Investigator to take simultaneously (at the same time): ZOF 30 mg (zofenopril calcium 30 mg) as one oblong film-coated tablet and AML 5 mg (amlodipine 5 mg) as one round tablet, according to Study Protocol.

Participants with SBP/DBP values classified as Grade 3 hypertension will be withdrawn from the study

Participants with uncontrolled BP (>130/80 mmHg) are provided with one treatment Patient Kit made up by:

иемани	Согр	porate Medical Departm	ent
Identification Number	Version Number	State	Effective date
FORM-000050125	2.0, CURRENT	Effective	08, Jan 2021

- o ZOF 30 mg: one labelled box (green label) containing 42 film-coated tablets (3 blisters with 14 film coated tablets each) of zofenopril calcium 30 mg
- o AML 10 mg: one labelled box (green label) containing 42 tablets (3 blisters with 14 tablets each) of amlodipine 10 mg.

The two green labelled boxes are then sealed together into a transparent plastic film to identify the treatment Patient Kit.

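### Inclusion criterion 1 contradicts itself: its Grade 1-2 label caps BP at 179/109, but its numeric limits, joined by and/or, are met by Grade 3 readings such as 185/95 or 150/112

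*Protocol*

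**What the plan says.** **Entry.** Protocol 6.2.1, criterion 1, opens with Grade 1-2 hypertensive patients and, after a colon, gives the limits "with mean sitting SBP ≥140 mmHg and ≤179 mmHg and/or mean sitting DBP ≥ 90 mmHg and ≤109 mmHg at Screening". The synopsis has the same limits ("sitting SBP ≥140 mmHg and ≤179 mmHg and/or mean sitting"), and SAP 4.4.1 repeats them. Protocol 2.1 defines the label: "Blood pressure [BP] ranging from ≥140/90 mmHg to ≤179/109 mmHg". Grade 3 is defined with an *or*: SBP of 180 or more, or DBP of 110 or more (Protocol 2.1 and 5; SAP 4.1 and 8.1.2). None of the sixteen exclusion criteria in Protocol 6.2.2 sets an upper BP limit.

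**Later visits.** The scheme in Protocol 2.1 says that patients with Grade 3 "hypertension will be withdrawn from the study at Visit 2 and Visit 3". The same rule is in the synopsis ("At Visit 2 and Visit 3 patients with SBP/DBP value classified as Grade 3"), in Protocol 5 for each visit ("At Visit 2 patients with SBP/DBP values classified as Grade 3" and "At Visit 3 patients with SBP/DBP values classified as Grade 3"), in the dispensing text of Protocol 8, and in SAP 4.1, 4.2 and 8.1.2. Protocol 7.1 states it for Visit 3 only ("Participants with SBP/DBP values classified as Grade 3 hypertension will be withdrawn from the study").

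**Where the rule is absent.** Protocol 5.1 (Visit 2 and Visit 3 text), Protocol 7.1 (the opening paragraph on who qualifies for the assessment period, and the Visit 2 kit text), the list in Protocol 10, the Efficacy population wording (SAP 5.3.3, SAP 10.1 and Table 14.1.2 footnote 5), and Table 14.1.1 footnotes 2 and 3.

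**The concern.** The label and the numbers sit in one criterion and give different answers for the same patient. Because the numbers follow the label after a colon, a site can reasonably take them as its definition, and then no written ceiling stops a patient who exceeds one limit but meets the other limb.

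What is at stake is mainly safety at entry. Such a patient would start run-in on one drug, with no visit scheduled for 4 weeks ± 2 days. Other BP-modifying drugs are prohibited (Protocol 7.6), rescue medicine is listed as not applicable (7.7), and the home BP device is meant for COVID-19 restrictions (2.2). The trial's own rule would withdraw that patient at Visit 2 if still Grade 3, so admission at Visit 1 cannot be intended.

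There is a smaller data consequence. SAP 5.4, Table 14.1.3 and Table 14.2.4.4.1 provide for hypertension Grades 1 and 2 only, so a Grade 3 entrant has no correct row or stratum.

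**Working it through.** **Inputs.** Criterion 1 numbers: SBP 140-179, and/or DBP 90-109 (Protocol 6.2.1). Grade 3: SBP ≥180 or DBP ≥110 (SAP 8.1.2).

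**Rules compared.**
- Current numbers: (140 ≤ SBP ≤ 179) or (90 ≤ DBP ≤ 109).
- Strict *and*: (140 ≤ SBP ≤ 179) and (90 ≤ DBP ≤ 109).
- Reworded: (SBP ≥140 or DBP ≥90) and SBP <180 and DBP <110.

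| Reading | Grade 3? | Current numbers | Strict *and* | Reworded |
|---|---|---|---|---|
| 185/95 | yes | met | not met | not met |
| 150/112 | yes | met | not met | not met |
| 185/85 | yes | not met | not met | not met |
| 135/112 | yes | not met | not met | not met |
| 185/112 | yes | not met | not met | not met |
| 150/95 | no | met | met | met |
| 150/85 | no | met | not met | met |
| 135/95 | no | met | not met | met |

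The current numbers reject 185/85 and accept 185/95, although the second patient has the higher diastolic pressure. Replacing and/or with *and* would close the gap but lose isolated systolic (150/85) and isolated diastolic (135/95) hypertension, which the criterion plainly means to include. Separate ceilings do neither harm.

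**Whole-number check.** Over SBP 100-220 and DBP 50-130 with SBP above DBP, the current numbers accept 1,660 Grade 3 combinations. The reworded rule accepts none, removes only Grade 3 readings and adds no one. These are cells of a grid, not patients.

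**Unrounded means.** Protocol 8.1 takes the visit value as the mean of three readings, so 179.33 can occur. It is not Grade 3, yet it fails a limit of ≤179. With <180 and <110, every reading is on one side or the other of the Grade 3 boundary. The only readings this adds are of the type 179.33/85 or 135/109.33, which lie between the two sets of limits and are not Grade 3.

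**Why no frequency is given.** The documents contain no screening BP distribution. Under an assumed bivariate normal, the share of patients meeting the numbers who are Grade 3 is:

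| SBP mean/SD | DBP mean/SD | r | Share |
|---|---|---|---|
| 150/10 | 92/8 | 0.3 | 1.64% |
| 155/11.5 | 93.5/8 | 0.45 | 3.53% |
| 160/13 | 95/8 | 0.3 | 8.52% |
| 155/11.5 | 93.5/6 | 0.45 | 1.95% |
| 150/10 | 92/6 | 0.45 | 0.35% |

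Moving the diastolic SD from 8 to 6 nearly halves the central value (3.53% to 1.95%), and if sites apply the label the share is zero. The range reflects the assumptions and does not measure the problem.

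**Visit 2 and the Efficacy population.** SAP 5.3.3 requires a post-baseline assessment from Visit 3 or 4. A patient withdrawn as Grade 3 at Visit 2 has none and is already outside the population. If the rule is followed, adding it to that definition changes nobody's status.

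**The case against.** The strongest reply is that the criterion already bars these patients. Its opening words are part of it, Protocol 2.1 gives them a ceiling, and Protocol 5 and 6 describe the patients to be screened as Grade 1-2. IWRS registration follows confirmation of all criteria (Protocol 8), and exclusion 12 leaves room for investigator judgement. This stands as far as it goes: harm needs a site to treat the numbers as the whole definition. It does not remove the inconsistency, because the label and the numbers cannot both be right for 185/95.

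A second reply is that the missing withdrawal statements are mostly editorial. That is largely correct. The rule is in operative text for both visits (Protocol 5 and 8), 7.1 refers to Section 5 for the design, and the general withdrawal reasons in Section 10 are not exhaustive. A reader might infer that sections without the rule direct sites to keep or up-titrate Grade 3 patients. The documents do not support that: these are silences, and none instructs the opposite.

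A reader might also infer that a known fraction of enrolled patients will be Grade 3, or that the primary result is compromised. Neither follows. No document supplies the distribution, and a Grade 3 entrant who is still Grade 3 at Visit 2 never reaches the primary analysis.

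**Conclusion.** Criterion 1 is internally inconsistent as written, in three places, and should be corrected. This rests on the text alone: 185/95 and 150/112 meet the numbers and are Grade 3 under the protocol's own definition, and no exclusion criterion catches them. The consequence is a possible four-week monotherapy run-in for a patient whom the trial would withdraw at the next visit. The label and investigator discretion reduce that risk, and its frequency cannot be estimated from the documents. The effect on the primary estimate is likely small.

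The uneven statement of the withdrawal rule is secondary. Its one visible reporting effect is in Table 14.1.1, where a Grade 3 withdrawal fits neither the Visit 2 nor the Visit 3 exclusion category as footnoted. It would fall under a reason such as lack of efficacy or other.

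**What to change.** **Main change.** In Protocol 6.2.1, the synopsis and SAP 4.4.1, reword the BP part of criterion 1 to: *(SBP ≥140 and/or DBP ≥90) and SBP <180 and DBP <110*. Do not simply replace and/or with *and*.

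**Secondary alignment.** Repeat the existing Grade 3 withdrawal rule in Protocol 5.1 (Visits 2 and 3), in 7.1 (opening paragraph and Visit 2 kit text) and in Section 10, and name Grade 3 in Table 14.1.1 footnotes 2 and 3. Adding it to SAP 5.3.3, SAP 10.1 and Table 14.1.2 footnote 5 is for consistency only.

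**Cost.** Wording in a protocol amendment and a SAP update, plus table footnotes. If the amendment is classed as substantial, Protocol 12.6 requires ethics committee and authority approval in the participating countries (three are listed), so the drafting is light but the process may not be. The sample size and the intended population do not change.
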